Intervention. Family Connections(FC)²⁰ focuses on parents as an agent of change. It includes two parent classes, followed by 10 IVR automated telephone support calls over 6 months. This intervention incorporates evidence-based principles⁸³⁻⁸⁹ with the goal to provide parents with the skills and confidence to change the physical and social environment to be supportive of healthy behaviors. Program materials are provided in a parent workbook with activities to be completed at home that align with IVR calls to promote increased physical activity and consumption of fruits and vegetables in concert with

decreased sugary-drink consumption and screen time. The program starts with 2 small group support sessions spaced one week apart that guides participants through developing an action plan for parental behaviors, role modeling, and changes to the home environment that would facilitate healthy eating and physical activity. It is followed by 10 IVR calls (5-10 minutes) beginning with weekly (4), biweekly (4), and monthly (2) calls. We use the 5As model⁹⁰ to help train parents in setting physical activity and healthful eating goals with their family during our IVR calls. This model includes **Assessing** behaviors and motivation, providing **Advice** on healthy behaviors, collaboratively **Agreeing** on goals, **Assisting** parents with barrier identification and resolution, and **Arranging** for follow-up⁹⁰. During each IVR call parents provide information on current physical activities, and food consumption. This information is compared to families goals for weight loss, physical activity, and food consumption and used to provide feedback on success in subsequent IVR calls. Calls also allow parents to select specific messages related to intervention content and help them prepare for relapse prevention (Calls 7-10) once the program is completed.

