Specific Aim 2: To evaluate the feasibility and preliminary effectiveness of a technology-delivered FBCO intervention for L/H families in rural Nebraska using RE-AIM and i-PARIHS. We will randomly assign participants to either the intervention or an enhanced standard care group (Figure 3). Sample Size Calculation. Sample size is based on the comparison of changes in BMI z-scores achieved by participants in FC-IVR with those achieved by participants in FC-workbook condition at 6 months post randomization²⁰. A total of 46 (23 per group) parent-child dyads achieves 80% power (alpha 0.05) to detect a significant difference between SC and IVR groups conditions. To account for a 25% attrition rate at 6-month we will recruit a total of 58 (29 per group) dyads. Participant Recruitment and Baseline Assessment Procedures. [name] will coordinate the recruitment of the participants with the help of CHWs. We will recruit a total of 58 dyads (Table 1). Baseline visits will take place at local community centers using private rooms. Dyads will complete informed consent, height, weight and waist circumference assessments, as well as complete a computer-based survey. Randomization will follow a random-numbers table (families/staff unblinded). Standard-Care. Families randomized to this group will receive FC-workbook. No additional materials or intervention contact will be provided. CHWs will follow a retention protocol to ensure these individuals return to 6-month assessments. Intervention Delivery. Families randomized to this group will receive the adapted version of the intervention described above. Drs. [name] and [name] will monitor IVR completion reports and assist the student-worker and CHWs in the on-going monitoring and engagement of participants during the intervention. Measurements and Data Collection. All measures (see table at PHS section for description) will be collected prior to intervention initiation and at 6 months post baseline (Figure 3). Weight will be assessed using a digital scale calibrated for accuracy prior to each assessment period using standard weights of a known quantity (e.g., 100-pound dumbbell). Height will be measured with a stadiometer, calibrated in 0.1-cm intervals. Waist circumference will be measured with a spring-loaded cloth tape measure at the level of the iliac crest using the average of the two closest measurements. Other Measures. Children and parents will complete measures of physical activity^{98,99}, eating behaviors¹⁰⁰, beverage intake¹⁰¹, quality of life^{102,103} acculturation^{104,105}, and health literacy¹⁰⁶. Parents will also complete home environment¹⁰⁷ surveys. During the 6-month assessment parents will complete program satisfaction surveys and a short exit interview with a CHW. Feasibility will be assessed according to intervention relevant factors (RE-AIM dimensions, engagement, attendance and completion rates), cost-effectiveness, cultural

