
relevance (aim 1 measures) and acceptability identified in exit survey/interviews to determine whether intervention is appropriate for further testing. Qualitative Analysis. Qualitative interviews and FGs will be recorded and transcribed in English or Spanish. The PI, with assistance from [name] and [name] will construct the interview codebook, with inductive codes added iteratively by in-depth reading of transcriptions until saturation is achieved. Transcripts will be double-coded in NVivo by [name], [name] and the PI. Inter-coder reliability using Cohens kappa (goal > 0.80) will be assessed. The research team has extensive experience conducting qualitative investigation^{20,22,26,51,58,62,67}, possesses local linguistic expertise (Drs. [name] and [name], speak Spanish), and will be aided by bilingual (English-Spanish) CHW staff. Statistical Analysis: The association of the intervention with the primary outcome of proportion of children reducing BMI z-scores will be tested using a chi-square test. The degree of association will be summarized using the odds ratio. If the assumptions of the chi-square test are violated, Fishers exact test will be utilized. Potential gender, and acculturation scores (external and familial language use, and social relations) differences will be explored via stratification. Comparisons between groups within gender will be done using Fishers exact test. Secondary aims outcomes include parent BMI, waist, PA, sweet beverages intake and eating behaviors, home environment changes and quality of life. The quantitative outcomes will be summarized using means and standard deviations or medians and inter-quartile ranges, as appropriate. If categorized, outcomes will be summarized using counts and percentages. Between group differences at 6-month will be capture using ANCOVA with the baseline measure as the covariate. If the ANCOVA assumptions are violated, a t-test (or if indicated, Wilcoxon's sum rank test) between group change scores (6-month baseline measure) will be used. Potential parental engagement (% of reach, retention and completion) and acculturation scores (language and media use, and social ethnic relations) differences will be explored via stratification. Comparisons between groups will be done using Fishers exact test. Significance level is 0.05.

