All questionnaires and biomarkers will be entered into a secure site through the Internet. All data will be entered in the firewall-protected server. The UNMC Research IT Office instructs investigators in its use and hosts the REDCap database of project data.

C. Select any of the following that apply to the research:

Phase I study

♦ Randomization

Placebo (or non-treatment arm)

Washout

Sensitive surveys or questionnaires

None of the above

Describe randomization process and schedule

Randomization will occur at enrollment and follow a random-numbers table (families/staff unblinded).

D. Identify:

1. All procedures, interventions, evaluations and tests performed solely for research purposes (eg, administration of an investigational drug or a new psychological assessment instrument; randomization)

With the exception of the standard care condition, all aspects of this study described above will be performed for research purposes. These include:

1. Eligibility and screening process
2. Monitoring of recruitment and retention of participants
3. Assessments / Measurements

2. All procedures, interventions, evaluations and tests performed for clinical indication but more frequently than they would be if the subject was not participating in the research (eg, extra blood tests; additional radiology exams)

We typically do not use assessments taken as part of normal clinical care, however, information provided by intervention and anthropometric tests performed (e.g. weight, height) are part of the usual care for both and children in a regular primary care practices.

E. Describe briefly the statistical methods used to analyze the data (or reference the appropriate section of the detailed protocol or grant).

A mixed-methods feasibility study will be used to address our 2 Aims:

Specific Aim 1 Design and Analyses

Cultural relevance Analysis: We will conduct an assessment of both the original intervention and the adapted intervention by in-depth interviews and focus groups to assess changes proposed to match the characteristics and preferences of potential participants. The English and Spanish versions of the Cultural Relevance Questionnaire (CRQ) and i-PARIHS will be

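### As most naturally read, an exploratory analysis compares the arms within levels of parental engagement, a post-randomisation variable, so selection alone can produce apparent benefit or harm

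*Combined protocol and SAP*

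**What the plan says.** The text is in section 12.B, Specific Aim 2, Statistical Analysis.

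- **Primary outcome.** Gender and acculturation are to be explored by stratification, and then "Comparisons between groups within gender will be done using Fishers exact test".
- **Secondary outcomes.** After the ANCOVA and its fallback tests comes a similarly built sentence. Its subject is "Potential parental engagement (% of reach, retention and completion) and acculturation scores", and it continues, after listing the acculturation subscales, "differences will be explored via stratification. Comparisons between groups will be done using Fishers exact test. Significance level is 0.05".

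Four other places bear on it.

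- Section 12.C places randomisation at enrolment, with families and staff unblinded.
- Section 12.B describes what FC families can complete: "It includes two parent classes, followed by 10 IVR automated telephone support calls over 6 months".
- Section 12.B describes SC as the workbook alone: "No additional materials or intervention contact will be provided". It does name a retention protocol to bring SC families back at 6 months.
- The Aim 2 hypothesis in section 2 expects FC to raise engagement, which it spells out as reach, retention and completion.

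No section defines completion for SC, confines the engagement analysis to FC, calls it non-causal, or gives a method for selection after randomisation. The statistical analysis text in section 12.E does not mention engagement strata.

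**The concern.** A test of FC against SC within a stratum answers a causal question only if the two arms are exchangeable within that stratum. Randomisation secures this for gender or for acculturation measured at baseline. It does not secure it for retention or completion, which are observed later and may depend on the arm.

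A high-completion stratum would hold motivated, self-selected FC families. Whatever SC families are placed beside them were not selected in the same way, because SC has nothing equivalent to complete. The low-completion stratum has the opposite imbalance. Fisher's test could then reject when FC does nothing.

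At stake is the interpretation of a feasibility study meant to show whether the programme merits further testing. A finding that FC works when parents engage, or harms those who do not, could be carried into the next trial on selection alone.

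**Working it through.** **1. When each stratifier is fixed.**

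| Variable | Fixed before randomisation? | Defined in both arms? |
|---|---|---|
| Gender | yes | yes |
| Acculturation at baseline | yes | yes |
| Reach (a participation rate) | yes | not a property of a randomised family |
| Retention | no | yes, but FC is expected to change it |
| Completion of classes and calls | no | FC only |

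Only retention and completion raise the problem. Families not retained have no 6-month outcome, so stratifying on retention amounts to a completers-only comparison.

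**2. The plan's own figure.** The plan gives no figure for this analysis. Its sample size (difference 0.05, SD 0.06, two-sided 0.05 assumed, 80% power) reproduces: 2 × (1.960 + 0.842)² × (0.06/0.05)² = 2 × 7.85 × 1.44 = 22.6, so 23 per group. Recruiting 29 per group and losing 25% leaves 29 × 0.75 = 21.75, about 22 per arm.

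**3. Simulation with no FC effect, 22 per arm.** In both arms the outcome is y = r·u + √(1 − r²)·e. Here u is the motivation that drives completion and r is an assumed correlation. FC is split at its median u, each half is compared with all of SC, and y is dichotomised at its mean. There were 6,000 trials per setting; ranges are over repeat runs.

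| r | At least one Fisher test rejects |
|---|---|
| 0 | 5.2–5.5% |
| 0.3 | 8.9–9.8% |
| 0.4 | 13.5–13.6% |
| 0.5 | 19.2–19.3% |

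A single stratum rejects in 4.6% at r = 0.3 and about 10% at r = 0.5. Fisher on all families as randomised rejects in 2.1–2.5%. If both arms are instead split at the median by the same process, at least one stratum rejects in only 3.0–3.8% at r = 0.3 to 0.5 (3.4% at zero).

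**4. Closed-form check of the bias.** With a split at the population median, the upper half of FC exceeds SC by r·√(2/π) = 0.798r SD, which is 0.24, 0.32 and 0.40 for r = 0.3, 0.4 and 0.5. The simulations gave 0.22–0.23, 0.30–0.31 and 0.38–0.39. As a success proportion the excess is arcsin(r)/π, or 9.7, 13.1 and 16.7 percentage points; the simulations gave 9, 12–13 and 16–17. Sample size does not enter either formula, so a larger trial would not remove the bias.

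**5. A second model, 29 per arm, 10,000 trials, no FC effect.** Half the families are motivated. Engagement and success rates are all assumed and, where two are given, are for motivated / other families. SC engagement is 75% regardless of motivation unless stated.

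| FC engagement | Success rate | Engaged stratum rejects | Either stratum rejects |
|---|---|---|---|
| 60% / 60% | 50% / 50% | 3.0% | 5.5% |
| 90% / 30%, SC identical | 70% / 30% | 3.2% | 5.6% |
| 90% / 60% | 70% / 30% | 3.8% | 6.9% |
| 90% / 30% | 60% / 40% | 4.4% | 7.5% |
| 90% / 30% | 70% / 30% | 6.9% | 12.4% |
| 90% / 20% | 80% / 20% | 16.7% | 26.9% |

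For the fifth row, true success among engaged FC families is (0.5 × 0.9 × 0.7 + 0.5 × 0.3 × 0.3) / (0.5 × 0.9 + 0.5 × 0.3) = 0.36/0.60 = 60%, against 50% in SC. Among non-engaged FC families it is (0.5 × 0.1 × 0.7 + 0.5 × 0.7 × 0.3) / 0.40 = 0.14/0.40 = 35%, again against 50%. At 200 per arm the engaged-stratum rejection in this row rises to about 35% (500 trials). Fisher on all randomised families at 29 per arm stays at 2.2–2.8% throughout.

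**The case against.** **The sentence may mean something else.** It may intend engagement to be compared between arms as an outcome. Engagement is written as percentages, which suit Fisher's test, while the quantitative secondary outcomes already have ANCOVA, a t-test or Wilcoxon. Section 2 treats the same three components as something FC should improve. Reach cannot sort randomised families into strata. The sentence also lacks the within-stratum phrase of its gender counterpart and does not define its groups. These cues are real, and a reader should not infer that the plan explicitly orders FC-versus-SC tests within completion levels. Still, engagement shares a subject and verb with acculturation, which is a stratifier, and the method named is stratification. The text needs settling on either reading, because completion cannot be compared with an arm that has nothing to complete.

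**The scheme in step 3 is not in the plan.** The plan gives no cut-point and no rule for placing SC families. Retention, moreover, exists in both arms. This stands: the excess requires engagement to be related to outcome and to operate differently by arm. Section 2 and the content of the two arms make a difference by arm likely, but give no measure of its strength.

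**The step is exploratory.** This also stands. A reader might infer that the trial's main result is compromised. The documents do not support that: the primary chi-square test and the secondary ANCOVA in section 12.B, and the mixed model in section 12.E, all compare the arms without engagement strata.

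**Conclusion.** The concern holds on the most natural reading of the sentence. Comparing FC with SC within levels of retention or completion conditions on a consequence of allocation and can show false benefit or harm. Nothing elsewhere in the documents prevents it.

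The size is conditional. With 22 per arm, no FC effect, and FC halves each set against all of SC, the chance of at least one Fisher rejection is about 9–19% at assumed correlations of 0.3–0.5, against about 5% at zero. Mild selection adds little (3.8% in the engaged stratum, 6.9% in either). An identical engagement process in both arms adds nothing.

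It would be tempting to say that the analysis will mislead. The documents give no correlation, engagement rate or stratum rule, so they support only that it can. This is an inexpensive correction to an exploratory analysis and does not challenge the primary comparison.

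**What to change.** In section 12.B, Specific Aim 2, Statistical Analysis:

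- Remove parental engagement as a stratifier of FC-versus-SC outcome comparisons. Keep only gender and acculturation, and state that the baseline acculturation score is used, since it is measured at both visits.
- Compare the arms as randomised.
- Compare retention between arms as an outcome among all 58 randomised families; Fisher's test is suitable for that.
- Report completion, and its relation to outcomes, descriptively within FC only and labelled observational.

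A complier-average estimate (the as-randomised difference divided by the proportion completing, with an interval) is optional. It must state its exclusion restriction, namely that assignment to FC has no effect on families who do not complete. Partial exposure to the classes and calls may violate this. The interval will be wide: if half complete, an assumed figure, dividing by 0.5 doubles its width even with that proportion treated as known.

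The cost is a few sentences of wording. No new data are needed, and nothing is lost from the primary analysis.

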a culturally adapted technology-delivered FBCO intervention for L/H families in rural Nebraska. Applying an iterative collaborative process, we will use a mixed-methods approach to culturally adapt FC to better fit the rural L/H community profile. A Community Workgroup facilitated by our rural partner organizations in Nebraska with a high population of L/H residents and theory-and data-driven approach using structured community input adaptation process will be conducted to develop and evaluate the relevance (ecological validity and equivalence), acceptability, and usability of all the adaptations made. We hypothesize that this process will lead to a program that is relevant, acceptable, and usable by L/H families in rural communities.

Aim 2: To evaluate the feasibility and preliminary effectiveness of a technology-delivered FBCO intervention for L/H families in rural Nebraska using RE-AIM and i-PARIHS. We will randomly assign participants to either FC (n=29) or an enhanced standard-care (SC) group (n=29) and determine overall study reach, preliminary effectiveness in reducing child BMI z-scores, potential for program adoption, implementation, and sustainability through local health departments (RE-AIM outcomes). SC participants will receive a workbook. FC participants will receive a workbook, 2 in person group sessions followed by 10 IVR calls over a period of 6 months. We hypothesize that a culturally adapted FC program will lead to a higher engagement (reach, retention and completion), significant higher proportion of L/H children reducing their BMIz scores at 6 months when compared to SC group, align (social validity) with health department perceptions of i-PARIHS constructs (Innovation, context, recipient characteristics), and that FC participants will view the intervention positively (i.e. relative advantage, observability, trialability, complexity, compatibility).

3. Background and Rationale

Describe the background of the study. Include a critical evaluation of existing knowledge, and specifically identify the information gaps that the project is intended to fill.

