
CHARACTERISTICS OF THE SUBJECT POPULATION

4. Accrual

A. Is this study conducted solely at sites under the oversight of the UNMC IRB (e.g.

UNMC, Nebraska Medicine, CHMC, UNO)?

Yes

1. How many subjects will need to be consented (per group, as applicable) in order to achieve the scientific objectives of the research?

The proposed study will involve approximately 272 (Aim 1=106, Aim 2=166) participants. Participants are required to complete study aims as described:

Aim 1:

We will involve 40 adults-parents from L/H families from the sampling region to participate in two rounds of focus groups (FG, n=80) with 6 parents taking part in usability tests (UT, n=6), and approximately 10 adults to participate in a Community Working Group (CWG, n=10) that will participate in two interviews (n=10).

Aim 2:

The parent-child dyads (n=116) include adults (19 years of age or older, n= 58) and their children (6-12 years of age, n=58) living in rural Nebraska over a period of 12 months and 2 different stages of the project randomized in two arms:

Standart Care= 29 dyads (58 participants)

FC intervention= 29 dyads (58 participants)

At the end of the intervention parents participating that participated in the intervention (FG, n=40) and CWG (n=10) will be invited to participate in focus groups for a post-program satisfaction and evaluation.

2. What is the statistical or other justification for the total number of subjects described above?

Aim 1 sample based in the literature recommended number per evaluation for focus group (5-10 participants) and usability tests (5 per test)⁷⁴.

Intervention testing sample size is based on the comparison of changes in BMI z-scores achieved by participants in FC-IVR with those achieved by participants in FC-workbook condition at 6 months post randomization14. A total of 56 (23 per group) parent-child dyads achieves 80% power (alpha 0.05) to detect a significant difference between the SC and IVR conditions, based on the relative BMI z-score differences (0.05) and standard deviation related to 6-month BMI z-score reduction for FC-IVR (0.06). To account for 25% rate at 12-month, we will recruit a total of 58 (29 per group) dyads.

5. Gender of the Subjects

A. Are there any enrollment restrictions based on gender?

No

6. Age Range of Subjects

A. Will adults be enrolled ?

Yes

1. What is the age range of the adult subjects?

19 years of age or older.

2. What is the rationale for selecting this age range?

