Maintenance	
 - Characteristics of completers vs non-completers - Intention to continue the intervention - Qualitative feedback on barriers/facilitators from participants/staff and leadership using i-PARIHS constructs 	
 -Demographic and clinical data from intake surveys [SW, CHWs] -Clinical data forms at 0,12 months [CHWs] -Qualitative interviews with participants, facilitators, staff, and health authorities [[name] , PI [name]] 	

Sample Size Calculation. Sample size is based on the comparison of changes in BMI z-scores achieved by participants in FC-IVR with those achieved by participants in FC-workbook condition at 6 and 12-month post randomization. A total of 46 (23 per group)

parent-child dyads achieves 80% power (alpha 0.05) to detect a significant difference between the FC-workbook and FC-IVR conditions, based on the relative BMI z-score differences (0.05) and standard deviation related to 6-month BMI z-score reduction for FC-IVR (0.06). To account for 25% attrition rate at 12-month, we will recruit a total of 58 (29 per group) parent-child dyads.

Cost Analysis: Costs will be assessed using time tracking spreadsheets and focused primarily on Aim 2 as it relates to the intervention delivery, though costs of participant recruitment will also be tracked using material and staff time to determine dollar amounts. [name] will complete A simple cost benefit analysis by assessing intervention implementation costs at 6-month post baseline by BMI z-scores reduction categories of unchanged, ≤ 0.1 , 0.1-0.25 and ≥ 0.25 , respectively.

Qualitative Analysis. Qualitative interviews will be recorded and transcribed in English or Spanish. The PI, with assistance from Drs. [name] and [name], will construct the interview codebook, with inductive codes added iteratively by in-depth reading of transcriptions until saturation is achieved. Transcripts will be double-coded in NVivo by [name]. Inter-coder reliability using Cohens kappa (goal > 0.80) will be assessed. The research team has extensive experience conducting qualitative investigation, possesses local linguistic expertise (Drs. [name] speak Spanish), and will be aided by community partners bilingual (English-Spanish) CHW staff.

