Health Departments (CDHD, ECDHD, TRPHD, CAPWN) will provide adequate space to allow for physical privacy when the participants discuss their informed consent and have

their risk assessments taken. All four Health Departments has an Automated External Defibrillator on site in the event of an emergent cardiac event. The PI ([name]) and at [name] will be at all for CWG in-person meetings and focus group, and the trained CHWs will present for participants in obtaining informed consent, conducting trainings for at home assessments. The PI and [name] are registered nurses, and the CHW are trained to provide first aid and emergency response action if needed. All investigators at each UNMC campus (Norfolk, Omaha) have password protected laptops, IT support, and private, locked office space. The principal investigator has two digital audio recorders. The grant will permit purchase of scales, stadiometers, iPads, and other equipment needed for baseline biomarker measures taken at the assessment points. A locked briefcase will be used to transfer hard copies of written study materials from the data collection site to the college.

Please see "Facilities and Other Resources" file from NIH proposal uploaded for more information.

LITERATURE REVIEW

34. References

Provide a full listing of the key references cited in the background (Section II.3). The references should clearly support the stated purpose of the study.

Please see "Bibliography and References" file from NIH proposal uploaded.

SECTION III

SUBMISSION DEADLINE

A. Full Board Review:

The IRB meets twice monthly, on the first and third Thursday of the month, with the exception of January and July when the IRB meets only on the third Thursday of the month. No more than 15 applications (e.g., initial review of a new study, re-review of a tabled study) will be reviewed at each meeting. All reviews are performed on a first-come first-served basis. The IRB meeting schedule and deadline dates can be found on the IRB website at www.unmc.edu/irb.

B. Expedited Review

Applications that qualify for expedited review have no submission deadline and can be reviewed independent of the IRB meeting schedule. Call the Office of Regulatory Affairs for assistance in determining if your study meets the requirements for expedited review.

ADDITIONAL REVIEW REQUIREMENTS

Final IRB approval and release of studies is contingent upon approval by the following UNMC committees or departments. Check the appropriate boxes:

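### The allocation method gives no concealment, list holder or site stratification, although the community health workers who recruit families also do the in-person assessments at four partner sites

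*Combined protocol and SAP*

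**What the plan says.** Item 12.C, which asks for the randomisation process and schedule, answers in one sentence: "Randomization will occur at enrollment and follow a random-numbers table (families/staff unblinded". The Specific Aim 2 text in 12.B has "Randomization will follow a random-numbers table (families/staff unblinded", placed after the account of consent and baseline measures. Neither mentions blocking, stratification, who prepares or keeps the list, or any concealment step. The manual of procedures announced in 12.B does not list randomisation among its topics.

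Arm sizes are given as fixed numbers. The aims state "We will randomly assign participants to either FC (n=29) or an enhanced standard-care (SC) group (n=29", and section 4 (Accrual) has "FC intervention= 29 dyads (58 participants".

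Four partner organisations take part; section 33 says "Health Departments (CDHD, ECDHD, TRPHD, CAPWN) will provide adequate space". CHWs recruit families they already work with (section 25) and take part in screening and in reviewing the consent form (section 29). Section IV, item 4, gives them all in-person assessments, although section 29.C has the authorised investigators carry out the screening measurements.

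The chi-square test of the primary outcome in 12.B is not adjusted for site, and the mixed model in 12.E names no site term.

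**The concern.** Blinding of families and staff is hardly possible here, but concealing the next assignment is. Concealment carries extra weight in this trial because the same group of workers meets families first, helps to judge eligibility and measures the child's height and weight, from which both eligibility and the outcome are derived. Section 21 also describes the programme's potential benefits as much greater than those of current care, so staff may have a preference. If a recruiter can see the next assignment, a family can be encouraged, delayed or discouraged accordingly, and no analysis reliably repairs that. The target difference is only 0.05 BMI z.

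The second risk is site imbalance. The four partners may differ in families, staff and measurement practice. If the arms are unevenly spread over them and no analysis adjusts for site, part of any difference between arms may be a difference between sites.

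**Working it through.** **Inputs.** 58 dyads, 29 per arm (section 4; 12.B; 12.E). Difference 0.05 and SD 0.06 in BMI z-score change (12.E). Four partner organisations (sections 33 and IV). Dyads per site are not given, so I assume 14/14/15/15, with 10/12/16/20 and 6/10/16/26 as the range.

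**The plan's own figure.** The plan states "A total of 46 (23 per group) parent-child dyads achieves 80% power (alpha 0.05", "based on the relative BMI z-score differences (0.05) and standard deviation related to 6-month BMI z-score reduction for FC-IVR (0.06". Two-sided normal approximation: n per arm = 2 × [0.06 × (1.960 + 0.842) / 0.05]² = 22.6, rounded up to 23. It reproduces.

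**Overall split if the table is used without restriction.** The number allocated to FC is Binomial(58, 0.5).
- P(exactly 29/29) = C(58,29) / 2^58 = 0.104.
- P(22/36 or more uneven) = 2 × P(X ≤ 22) = 0.087.

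**What an uneven split costs in power.** Two-sided t-test, all 58 analysed, 56 degrees of freedom, critical value 2.003, noncentrality = 0.05 / [0.06 × √(1/n₁ + 1/n₂)].
- 29/29: noncentrality 3.173, power 87.7%.
- 22/36: noncentrality 3.079, power 85.7%.

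The loss is about 2 points, at a split that would itself be unusual.

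**Balance within sites, unrestricted.**
- Site of 14: 2:1 or worse means 4/10 or more uneven, 2 × P(X ≤ 4) = 0.180.
- Site of 15: 5/10 or more uneven, 2 × P(X ≤ 5) = 0.302.
- At least one of four sites: 1 − (0.820)² × (0.698)² = 0.672.
- With 10/12/16/20 the figure is 72%; with 6/10/16/26 it is 85%.

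**Balance within sites if the table is used to draw a fixed 29/29 list.** The overall split is then exact, but the sites are still left to chance. The probability is 1 − Σ ∏C(mᵢ,kᵢ) / C(58,29), where mᵢ is the size of site i, kᵢ its number in FC, and the sum runs over site splits that add to 29 with none 2:1 or worse. It gives 49% for 14/14/15/15, 58% for 10/12/16/20 and 79% for 6/10/16/26.

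**Stratified permuted blocks.** Simulation, 20,000 runs, sites 14/14/15/15. A guess means naming the arm currently behind at the site.

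| Block sizes | Largest site difference | P(29/29) | Largest overall difference | Correct guesses |
|---|---|---|---|---|
| 2 and 4 | 2 dyads | 45% | 6 | 71% |
| 4 and 6 | 3 dyads | 38% | 8 | 68% |

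No site reached 2:1 under either scheme. Guessing under unrestricted allocation is right 50% of the time.

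**The case against.** A reader might infer that unblinded staff operate the table and that allocation is therefore foreseeable. The documents do not support that. The parenthesis about families and staff describes blinding, not who holds the list. An unrestricted random sequence cannot be predicted from past assignments; it is foreseeable only if recruiters can see it, which the plan neither states nor excludes. The supportable statement is that concealment is not described.

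The documents also do not call the scheme simple or unrestricted. A random-numbers table can be used to draw a list with exactly 29 per arm, which fits the stated arm sizes. On that reading the 10% figure does not apply, and the 67% falls to 49% under the same site sizes. Site imbalance remains likely, so this part of the objection narrows the point without removing it.

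Blocking makes prediction easier when staff know past assignments. That stands. It argues against blocks of 2, and larger varying blocks reduce the predictability only modestly (68% against 71% correct guesses). It is the price of site balance.

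The two statements on timing can be read together, because the baseline visit may be what is meant by enrolment. They need the same wording, but they do not contradict each other.

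Finally, this is a feasibility study with preliminary effectiveness as an aim, so stratification and a site term improve the design rather than correct an error. That is fair. Concealment, however, matters at any size.

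**Conclusion.** The point holds as a low-cost improvement. Sequence generation, custody of the list, concealment and stratification are not described, in a trial where CHWs recruit, help screen and assess across four sites. The reasons to act are possible selection bias and arm-by-site imbalance. Missing 29/29 is a minor matter, at about 2 points of power for a 22/36 split.

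The 10% and 67% figures assume unrestricted allocation, and the 67% also assumes near-equal sites. Over the site sizes tried, the chance of at least one site at 2:1 or worse is 67% to 85% without restriction and 49% to 79% with a fixed 29/29 list.

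Two further readings are tempting and should not be drawn. The size of any selection bias in BMI z units cannot be estimated, because the documents give no basis for one. Nor can it be said that a site would have too few FC families for its group sessions: the plan gives no minimum group size, no dyads per site, and no statement that sessions run separately by site.

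**What to change.** 1. Replace the table with a list generated by the study statistician, stratified by health department, in permuted blocks of varying and undisclosed size, without blocks of 2. Name who holds it, away from recruiting staff.
2. Release each assignment through REDCap, which already hosts the project data, only after consent and baseline measurements are recorded. Use sealed opaque envelopes when a rural visit is offline.
3. Write the order consent, baseline measurement, randomisation identically in 12.B and 12.C.
4. Include health department as a term in the BMI z-score model in 12.E.
5. Describe the arms as about 29 dyads each, since stratified blocks limit imbalance but do not guarantee 29/29.

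The cost is protocol wording, a short set-up and an offline back-up procedure. The drawback is some predictability from blocking at small open-label sites, which larger varying blocks limit but do not remove. The allocation changes must be in place before the first dyad is randomised.
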